6.2.2. Primary Effectiveness Endpoint

The primary effectiveness endpoint will be evaluated by the failure free rate collected at 12 months post-index procedure.

Failure defined as:

- Failure to achieve acute procedural success* in the index procedure;
- Any documented recurrent AF episode(s), or new onset of AFL or AT events (≥ 30 seconds in duration from any clinical recording devices **OR** from a 10-second 12-lead ECG) between Days 91 and 12-Month follow-up;
- Any of the following interventions between Days 91 and 12-Month follow-up:
 - Repeat AF ablation procedure;
 - Electrical and/or pharmacological cardioversion for AF or new AFL, AT;
 - Prescribed a higher dose of any AAD*** documented at baseline or a new AAD*** not documented at baseline.

* Acute procedural success is defined as isolation of all the pulmonary veins or anatomical equivalents achieved with the Cryoablation Catheter at the end of the index procedure and as demonstrated at minimum by entrance block using the Cryo Mapping Catheter (Other techniques of assessment are per investigator's discretion).

** Subjects will be monitored for recurrences/new onset of the arrhythmias by means of 12-lead ECG OR any clinical recording devices (for example but not limited to, smart watch, 24-hour Holter monitoring, home monitoring systems or implanted devices etc.) that are per standard of care (SOC) used by the hospital/clinic. These documentation of episodes would need to be verified by investigator and filed in medical records.

*** AADs for endpoint will consist of all Class I/III and any Class II/IV medications taken for control of AF/AFL/AT recurrence

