	
 • Pulmonary edema/heart failure • AV block not attributable to medication effect or vasovagal reaction. 
* Thromboembolic or air embolic events collected in the study refer to any occlusion of blood vessel(s) that results in clinical symptoms.
 
** Defined as prolongation of hospitalization, requirement of surgical intervention or blood transfusion.
 
Chronic primary safety endpoint events, events occurring through 12 months post-index procedure, include:
 
 • Atrial esophageal fistula • Significant pulmonary vein (PV) stenosis ($\geq 70\%$ reduction of diameter of the PV from baseline*** OR presented by patient's symptoms at 12-Month follow-up and requiring intervention) • Symptomatic pericardial effusion • Persistent phrenic nerve injury**** 
*** Recommended to use the same imaging method as baseline.
 
**** A non-recovered phrenic nerve injury at 12 months post-index procedure will count as a chronic primary endpoint. The study will collect information on phrenic nerve palsy observed before the end of the index procedure and, in case it occurred, will track information for potential recovery during the study visits.

Primary Effectiveness Endpoint	
Failure free rate at 12 months post-index procedure.
 
Failure defined as:
 
 • Failure to achieve acute procedural success* in the index procedure; • Any documented recurrent AF episode(s), or new onset of atrial flutter (AFL) or any other atrial tachycardia (AT) events (≥ 30 seconds in duration from any clinical recording devices OR from a 10-second 12-lead ECG) between Days 91 and 12-Month follow-up**; • Any of the following interventions between Days 91 and 12-Month follow-up: 
 ▪ Repeat AF ablation procedure; ▪ Electrical and/or pharmacological cardioversion of AF or any new AFL, AT; ▪ Prescribed a higher dose of any anti-arrhythmic drugs (AAD)*** documented at baseline or a new AAD*** not documented at baseline.

POLARx™ Cardiac Cryoablation System Post Market Clinical Study
POLAR SMART

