To collect continued effectiveness data of the Cryoablation System	Failure-free rate at 12 months including: i. failure to achieve success at index procedure, ii. documented AF/AFL/AT iii. interventions to treat these arrhythmias after blanking period, including repeated procedures cardioversion or prescription of new anti-arrhythmic drugs (or higher dose)	
Secondary		
Acute procedural success	Success of procedure (PVI)	Component of the primary effectiveness endpoint
To collect continued effectiveness data of the Cryoablation System	Failure-free rate at 6 months including failure to achieve success at index procedure, documented AF/AFL/AT or interventions to treat these arrhythmias after blanking period, including repeated procedures cardioversion or prescription of new anti-rrhythmic drugs (or higher dose)	To determine potential early benefits comparing to 12 months that has been established by the HRS consensus document.
Additional		
Quality of life assessment	Changes in the quality of life measures (AFEQT and EQ-5D-5L) between baseline and 12 months follow up	Relief from symptoms is one of the main ouotcomes reported of AF ablation

7. Study Design

The POLAR SMART study is a prospective, multicenter, single arm, post-market study.

All subjects signing the consent, undergoing the index (ablation) procedure and treated with the study devices will be followed up for one year.

7.1. *Scale and Duration*

- A minimum sample size of 200 subjects treated only with PVI is required. The maximum overall study sample size will be limited to ≤ 400 subjects.
- To avoid any center effect and bias, individual centers will not be allowed to enroll more than 20 subjects meeting enrollment criteria, unless Boston Scientific gives written approval to do so. The enrollment period is approximately 12 months.
- Approximately 30 sites in Japan and South Korea.
- Total expectation duration of study with all follow-up data collected is estimated to be approximately 36 months.
- The study duration for each subject is expected to be approximately 12 months. Each subject will be followed up at:
 - Enrollment and Baseline clinic visit, baseline visit can be the same day as enrollment visit, however the Informed Consent must be signed and dated prior to conducting any study related activities (up to 90 days before Index Procedure);
 - Index (Ablation) procedure (day 0);
 - Pre-discharge visit must be done before hospital discharge (required);

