9.4.4. Treatment

Any subject who has given written informed consent and has the specified study device inserted into the body and received at least one Cryoablation application will be classified as “TREATMENT”. These subjects are followed in accordance with the Data Collection Schedule (Table 10.1-1) and included in all study analyses. A subject ID will be assigned in the EDC system. For TREATMENT subjects, all applicable eCRFs per the protocol will be completed. Treatment subjects do count towards the overall enrollment ceiling and will be used for analyses of the endpoints. The original signed ICF and any relevant documentation must be maintained in the center’s subject file. Treatments will be further classified into the following subgroups:

- **PVI-only:** Subjects receiving treatment for PVI only or PVI and CTI.
- **PVI plus additional ablations (PVI+):** Subjects receiving treatment for PVI (or PVI and CTI), plus additional ablations at other anatomical location(s) in the right or left atrium intended to treat AF, AT or atypical AFL.

PVI-only subjects are included in all study analyses, with additional primary endpoint analyses being performed for PVI+ subjects as well as combined PVI-only and PVI+ subjects, as described in Section [11.2.1](#).

9.5. *End-of-Study Definition*

The clinical study is considered completed when subjects are no longer being examined or the last subject’s last study visit has occurred. The subject’s end of study is defined as completion of the last visit or procedure as shown in the Data Collection Schedule (Table 10.1-1) in the study.

10. Study Methods

10.1. *Data Collection*

The data collection schedule is shown in Table 10.1-1. Data collection will take place at the following time points:

- Informed Consent and Enrollment clinic visit
- Baseline clinic visit, can be the same day as enrollment visit, however the Informed Consent must be signed and dated prior to conducting any study related activities (up to 90 days before Index Procedure);
- Index (Ablation) procedure (day 0);
- Pre-discharge visit must be done before hospital discharge (required);
- 3 months follow-up visit (recommended in-clinic follow-up visit if done as per SOC, at a minimum a telephone contact follow-up is required.) This telephone contact follow-up would only be required if in-clinic follow-up was not done.

- 6 months follow-up visit (optional, this can be either a in-clinic follow-up visit or a telephone contact follow-up as per SOC.);

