10.11. Repeat ablation procedure

It is known that during the first 90 days post-index procedure (blanking period), subjects can suffer from recurrences of AF or onset of new AT. Within the blanking period, more than one repeat ablation procedure, using a commercially available ablation system, is allowed.

A repeat ablation procedure performed after blanking period will count as a failure for the primary effectiveness endpoint. During the repeat ablation procedure, the anatomical location of potential ablation gaps in the pulmonary veins will be assessed.

In case a repeat ablation procedure occurs during the 12 month follow-up period, the data of this procedure will be entered in the 'Additional Procedure' eCRF. In case this ablation procedure is performed to treat a supraventricular arrhythmia, including AF, AFL or AT, following detailed information about this repeat ablation procedure will be collected:

- Was the ablation procedure performed in the LA?;
- Was this repeat ablation procedure performed using BSC cryoablation?;
- For repeat ablation procedures performed in the LA: was this repeat ablation procedure performed to treat AF/AFL/AT? If no, specify the arrhythmia type;
- Rhythm at the beginning (12-lead ECG) and the end of the repeat procedure (documented by means of a post-ablation EGM/12-lead ECG);
- Reportable Adverse Events, including resolution of ongoing events, if applicable, and/or Device Deficiencies;
 - In cases of a pre-existing and unresolved phrenic nerve palsy the subject should be assessed to evaluate if the event resolved (method per investigator's discretion);
- Protocol deviations, if applicable.

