Myocardial infarction (in the context of AF ablation)	
The presence of any one of the following criteria:
 
(1) detection of ECG changes indicative of new ischemia (new STT wave changes or new LBBB) that persist for more than 1 hour;
 
(2) development of new pathological Q waves on an ECG;
 
(3) imaging evidence of new loss of viable myocardium or new regional wall motion abnormality

Occlusion Grade	
Score 4 = excellent (full retention of contrast medium without visible outflow)
 
Score 3 = moderate (incomplete occlusion with slight leakage of contrast medium)
 
Score 2 = poor (presence of sustained and massive leakage of contrast medium)
 
Score 1 = very poor (immediate rapid outflow from the PV).

Paroxysmal Atrial Fibrillation	Recurrent symptomatic Atrial Fibrillation that terminates spontaneously or with intervention within seven days of onset.
Pericardial Effusion	A collection of fluid or blood in the pericardial space around the heart or in pleural space around the lungs.
Pericarditis	Inflammation of the pericardium surrounding the heart. Pericarditis should be considered a major complication following ablation if it results in an effusion that leads to hemodynamic compromise or requires pericardiocentesis, prolongs hospitalization by more than 48 hours, requires hospitalization, or persists for more than 30 days following the ablation procedure.
Pneumothorax	Collapse of the lung due to an abrupt change in the intrapleural pressure within the chest cavity.
Primary Effectiveness Failure	
A TREATMENT subject with
 
 • Acute procedure failure • Documented atrial fibrillation, or new onset of atrial flutter or atrial tachycardia event (≥ 30 seconds in duration from an event monitor or Holter, or from a 10 second 12-lead ECG) between Days 91 and 12-month post index procedure • Any of the following interventions for atrial fibrillation, or new onset of atrial flutter or atrial tachycardia between Days 91 and 12-month post index procedure: 
 ○ Repeat AF procedure ○ Electrical and/or pharmacological cardioversion for AF/AFL/AT ○ Prescribed a higher dose of any AAD documented at baseline or a new AAD not documented at baseline
Procedural Success	Pulmonary vein isolation achieved with the Boston Scientific cryoablation system as demonstrated by entrance block at the minimum.

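### The primary effectiveness endpoint counts flutter and atrial tachycardia only when new, with no reference date, so a return of pre-existing AFL/AT counts or not according to how it is handled

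*Combined protocol and SAP*

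**What the plan says.** Section 6.2.2 defines the rhythm limb of failure as "Any documented recurrent AF episode(s), or new onset of AFL or AT events" from Day 91 to Month 12. The cardioversion limb reads "Electrical and/or pharmacological cardioversion for AF or new AFL, AT". Section 6.2.3 uses the same wording for the 6-month rate.

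The synopsis has "new onset of atrial flutter (AFL) or any other atrial tachycardia (AT) events", which can also be read so that the new-onset condition attaches to flutter alone. Table 23.2-1 has "Documented atrial fibrillation, or new onset of atrial flutter or atrial tachycardia event". None of these gives a date or state against which an arrhythmia is new.

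Other places are broader:

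- Table 6.2-1, describing the same endpoint, lists "ii. documented AF/AFL/AT iii. interventions to treat these arrhythmias after blanking period", with no new-onset condition.
- The antiarrhythmic drug (AAD) limb of 6.2.2 has no such condition. Section 10.4.1.1 makes a new or increased AAD for any AT after blanking a primary effectiveness failure.
- Section 10.11 counts a repeat ablation after blanking as a failure.

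On who is analysed, 9.4.4 defines PVI-only as "Subjects receiving treatment for PVI only or PVI and CTI", and 11.2.1 limits the main analyses to that group.

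**The concern.** AF counts whenever it is documented in the window, but AFL and AT must also be new. A subject whose pre-ablation flutter returns has a documented atrial arrhythmia after blanking and may still be reported as failure-free. Whether that happens depends on the response: a drug prescription makes the subject a failure, while an ECG record or a cardioversion does not. Failure status then follows treatment choice rather than rhythm.

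No hypothesis test is planned (section 11), so the 12-month failure-free rate is itself the main effectiveness result, and 11.3.5 plans a comparison of therapy success with POLAR ICE. With no reference date for new, two competent people could code the same subject differently on a primary endpoint.

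**Working it through.** **Step 1: can such subjects be in the main analysis?** No exclusion criterion in 8.3 names prior flutter or AT. Section 10.5.3 allows right atrial ablation at the index procedure, including CTI lines for flutter. Section 9.4.4 places PVI plus CTI in PVI-only, the main set. So they can.

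**Step 2: one subject, four outcomes.** Take a PVI plus CTI subject with flutter before the index procedure. It returns at day 200, with no AF.

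| What happens | 6.2.2, plain reading | Elsewhere |
|---|---|---|
| Documented only | Not a failure: not new | Table 6.2-1: failure |
| Electrical cardioversion | Not a failure: not new | Table 6.2-1: failure |
| New or higher-dose AAD | Failure | 10.4.1.1: failure (any AT) |
| Repeat ablation | Failure only if it is a repeat AF ablation | 10.11: failure |

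Table 23.2-1 adds a further variant. Its lead-in ties all interventions, AADs included, to AF or new-onset AFL/AT, yet its cardioversion line drops the word new.

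**Step 3: AFL/AT first seen in blanking.** Section 10.11 says that in the first 90 days "subjects can suffer from recurrences of AF or onset of new AT". If new means not present before the index procedure, its return after Day 90 counts. If it means first seen on or after Day 91, it does not. The text does not decide.

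**Step 4: direction.** Every failure on the plain reading is also a failure when any AFL/AT counts. The narrower wording can therefore only raise the proportion called failure-free, apart from small timing effects of censoring on the Kaplan-Meier estimate.

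**Step 5: size, pre-existing AFL/AT only.** The plan gives no expected rate or share, so there is no figure to reproduce. All inputs except the minimum of 200 subjects (7.1) are assumptions. The 70% is one of the two comparator efficacy figures in 4.1, used here for illustration.

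Shift = a × b × S, where a is the share with AFL/AT before the index procedure, b is the share of those otherwise failure-free whose only event is its return, and S is the failure-free rate.

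- Low: 0.05 × 0.05 × 0.70 = 0.2 points; 200 × 0.00175 = 0.4 subjects.
- Middle: 0.20 × 0.10 × 0.70 = 1.4 points; 200 × 0.014 = 2.8 subjects.
- High: 0.30 × 0.20 × 0.70 = 4.2 points; 200 × 0.042 = 8.4 subjects.

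With b taken instead as a share of all subjects with prior AFL/AT, 0.15 × 0.10 = 1.5 points, or 3 subjects. The range is 0.10 × 0.05 = 0.5 to 0.25 × 0.15 = 3.75 points.

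**Step 6: precision, for scale.** The log-log 95% limits named in 11.1.1.1, with no censoring, are exp(−exp(L ± 1.96 × SE)), where L = ln(−ln S) and SE = √[S(1−S)/n] / (S × |ln S|). At S = 0.70 and n = 200 the limits are 63.1% and 75.8%, a half-width of (75.8 − 63.1)/2 ≈ 6.4 points. At S = 0.75 they are 68.4% and 80.4%, a half-width of 6.0.

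**The case against.** **It may be deliberate.** The objective is PVI for de novo AF. The study system cannot be used outside the pulmonary veins, and CTI lines are made with another system (10.5.3). Not charging returning flutter to the study device is coherent. That stands as a possible design choice, but the plan does not state it, and the unrestricted AAD limb does not fit it.

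**New may mean a new episode.** The Table 10.1-1 row on new AF/AFL/AT cannot mean first-ever, since these subjects already have AF. That shows the word is loose. It does not displace the plain reading of 6.2.2, which sets recurrent AF against new-onset AFL/AT.

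**Table 6.2-1 is only an overview.** It also drops the 30-second threshold. A reader might infer two rival definitions, but the synopsis and the detailed definitions in 6.2.2 and Table 23.2-1 all carry the new-onset wording, so the table may simply be abbreviated. It still needs reconciling. The disagreement with 10.4.1.1 does not rest on it.

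**Other limbs catch some cases.** A reader might infer that every return of pre-existing flutter is failure-free. It is not: a new or higher-dose AAD, or a repeat ablation counted under 10.11, still makes the subject a failure.

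**Conclusion.** The point holds for one group: subjects with pre-existing AFL/AT that returns after Day 90, without AF, and is only documented or cardioverted. On the plain reading of 6.2.2 and 6.2.3 they are failure-free at 12 and 6 months, in conflict with Table 6.2-1 and out of line with the AAD rule.

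A reader might go further and infer that AFL/AT first seen in blanking is excluded as well. The documents do not say so. The reference date is missing, and 10.11 itself calls such AT new, so this is an ambiguity and no size is attached to it.

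The effect is about 1.5 points (roughly 0.2 to 4) at 200 subjects, resting wholly on assumed shares. It lies inside the interval half-width of about 6 points, but the interval describes sampling error and does not cover a definitional shift in one direction. No pass/fail decision turns on it. It should be fixed before analysis, but it does not undermine the study.

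**What to change.** - Use one definition in the synopsis, 6.2.2, 6.2.3, Table 6.2-1, 10.4.1.1 and Table 23.2-1, applied to both the rhythm and cardioversion limbs. The preferred form is any documented AF, AFL or AT after Day 90 that meets the existing recording criteria, whether or not it was present before the index procedure or first seen in blanking.
- If pre-existing or CTI-dependent flutter is deliberately left out, state that exclusion with its reference date, and report the 6- and 12-month rates both ways.
- Align data collection. The visit lists in 10.6 to 10.10 and the Table 10.1-1 row carry the same new wording, so a site could reasonably not record returning AFL/AT. Section 17.1 sends arrhythmia recurrences to a recurrence form, which helps, but the visit lists should ask for them outright. Otherwise the second rate may lack data.

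The cost is small edits to the wording and the eCRF instructions, and a slightly less favourable reported rate.

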6.2.3. Secondary Endpoints

- Rate of documented acute procedural success, defined as pulmonary vein isolation achieved with the Cryoablation System. Electrical isolation of a PV is demonstrated at minimum by entrance block using the Cryo Mapping Catheter (Other techniques of assessment are per investigator's discretion).
- Failure free rate collected at 6 months post-index procedure.
 - Failure to achieve acute procedural success* in the index procedure;
 - Any documented recurrent AF episode(s), or new onset of AFL or AT events (≥ 30 seconds in duration from any clinical recording devices **OR** from a 10-second 12-lead ECG) between Days 91 and 6-Month follow-up**;
 - Any of the following interventions between Days 91 and 6-Month follow-up:
 - Repeat AF ablation procedure;
 - Electrical and/or pharmacological cardioversion for AF or new AFL, AT;
 - Prescribed a higher dose of any AAD*** documented at baseline or a new AAD*** not documented at baseline.

* Acute procedural success is defined as isolation of all the pulmonary veins or anatomical equivalents achieved with the Cryoablation Catheter at the end of the index procedure and as demonstrated at minimum by entrance block using the Cryo Mapping Catheter (Other techniques of assessment are per investigator's discretion).

** Subjects will be monitored for recurrences/new onset of the arrhythmias by means of 12-lead ECG OR any clinical recording devices (for example but not limited to, smart watch, 24-hour Holter monitoring, home monitoring systems or implanted devices etc.) that are per standard of care (SOC) used by the hospital/clinic. These documentation of episodes would need to be verified by investigator and filed in medical records.

*** AADs for endpoint will consist of all Class I/III and any Class II/IV medications taken for control of AF/AFL/AT recurrence

6.2.4. Additional Endpoints

Additional endpoints and analyses include, but are not limited to:

- Procedure times: LA dwell time*, total ablation time, number of cryo applications per vein, time to thaw, total fluoroscopy time and total procedure time;
- TTI per ablation application, if available;
- Freedom from recurrence of individual types of AF, or new AFLs or ATs between Days 91 and 12-Month follow-up;
- Analysis of additional ablation techniques performed as there is foreseen CTI and roof line ablation performed with other catheters outside PVI;
- Analysis of different anaesthesia techniques (General anaesthesia with or without intubation versus sedation);
- Freedom from AF recurrence in subjects with anatomical variants of PV such as, but not limited to, common ostia, additional pulmonary vein or early branching;
- Freedom from primary effectiveness failure evaluated in subgroups of subjects (termination of AAD versus continuation of AAD after blanking period);
- For subjects undergoing 3D mapping with the Boston Scientific Rhythmia Mapping System and performing a post-procedural map, map information will be collected to determine lesion locations;
- The percentage of subjects that undergo repeat ablation during the course of the clinical follow-up;
- More than one repeat procedure during the blanking period (within 90 days post-index procedure);
- Changes in the quality of life measures (AFEQT and EQ-5D-5L) between baseline and 12 months follow up;
- The percentage of subjects experiencing device-related adverse events;
- Comparison of procedural and therapy success between POLAR ICE (NCT04250714) and POLAR SMART.

* LA dwell time is defined as time from the Cryoablation Catheter introduced in the LA to the last time of Cryoablation Catheter exiting the LA.

Table 6.2-1 Overview of objectives and endpoints

OBJECTIVES	ENDPOINTS	JUSTIFICATION FOR ENDPOINTS
Primary		
To establish continued safety of the cryoablation System in Asian geographies	Event free rate of a composite of procedure and device study specific adverse events (acute: 7 days and chronic: 12 months follow-up)	Majority of the BSC POLARx™ system studies data were collected predominantly in North American and European populations, it will be necessary to collect systematic scientific evidence unique to Japan and South Korea to proactively capture the impact on medical outcome driven by socio-economic, healthcare and epidemiological differences
To collect continued effectiveness data of the Cryoablation System	Failure-free rate at 12 months including: i. failure to achieve success at index procedure, ii. documented AF/AFL/AT iii. interventions to treat these arrhythmias after blanking period, including repeated procedures cardioversion or prescription of new anti-arrhythmic drugs (or higher dose)	
Secondary		
Acute procedural success	Success of procedure (PVI)	Component of the primary effectiveness endpoint
To collect continued effectiveness data of the Cryoablation System	Failure-free rate at 6 months including failure to achieve success at index procedure, documented AF/AFL/AT or interventions to treat these arrhythmias after blanking period, including repeated procedures cardioversion or prescription of new anti-rrhythmic drugs (or higher dose)	To determine potential early benefits comparing to 12 months that has been established by the HRS consensus document.
Additional		
Quality of life assessment	Changes in the quality of life measures (AFEQT and EQ-5D-5L) between baseline and 12 months follow up	Relief from symptoms is one of the main ouotcomes reported of AF ablation

7. Study Design

The POLAR SMART study is a prospective, multicenter, single arm, post-market study.

All subjects signing the consent, undergoing the index (ablation) procedure and treated with the study devices will be followed up for one year.

7.1. *Scale and Duration*

- A minimum sample size of 200 subjects treated only with PVI is required. The maximum overall study sample size will be limited to ≤ 400 subjects.
- To avoid any center effect and bias, individual centers will not be allowed to enroll more than 20 subjects meeting enrollment criteria, unless Boston Scientific gives written approval to do so. The enrollment period is approximately 12 months.
- Approximately 30 sites in Japan and South Korea.
- Total expectation duration of study with all follow-up data collected is estimated to be approximately 36 months.
- The study duration for each subject is expected to be approximately 12 months. Each subject will be followed up at:
 - Enrollment and Baseline clinic visit, baseline visit can be the same day as enrollment visit, however the Informed Consent must be signed and dated prior to conducting any study related activities (up to 90 days before Index Procedure);
 - Index (Ablation) procedure (day 0);
 - Pre-discharge visit must be done before hospital discharge (required);
 - 3 months follow-up visit (recommended in-clinic follow up visit if done as per SOC, at a minimum a telephone contact follow-up is required.) This telephone contact follow-up would only be required if in-clinic follow-up was not done;
 - 6 months follow-up visit (optional, this can be either a in-clinic follow-up visit or a telephone contact follow-up as per SOC)
 - 12 months in-clinic follow-up visit (required);
 - An additional follow-up visit at the investigational site is any subject visit triggered by subject symptoms, clinically events or per SOC that is not already defined as one of the study visits.

[figure not shown]

Figure 7.1-1: POLAR SMART Study Design

